#### ECG Findings That Qualify as SAEs

- Change in pattern suggestive of new myocardial infarction.
- Sustained ventricular tachyarrhythmias (>30 seconds' duration).
- Second- or third-degree AV block requiring pacemaker placement.
- Asystolic pauses requiring pacemaker placement.
- Atrial flutter or fibrillation with rapid ventricular response requiring cardioversion.
- Ventricular fibrillation/flutter.
- At the discretion of the investigator, any arrhythmia classified as an adverse experience.

The enumerated list of major events of potential clinical concern are recommended as “alerts” or notifications from the core ECG laboratory to the investigator and Pfizer study team, and not to be considered as all inclusive of what to be reported as AEs/SAEs.

## 10.8. Appendix 8: Abbreviations

The following is a list of abbreviations that may be used in the protocol.

Abbreviation	Term
®	ongoing/continuous event
%CI	confidence interval (%)
3CL	3C-like
3CL pro	3C-like protein
Abs	absolute
ADL	activities of daily living
AE	adverse event
AESI	adverse event of special interest
ALT	alanine aminotransferase
aPTT	activated partial thromboplastin time
AST	aspartate aminotransferase
AUC	area under the concentration-time curve
AUC inf	area under the plasma concentration-time curve from time zero extrapolated to infinity
AUC last	area under the plasma concentration-time curve from time zero to the time of the last measurable concentration
AUC tau	area under the plasma concentration-time profile from time zero to time tau ( $\tau$ ) the dosing interval, where tau=12 hours for BID dosing
AV	atrioventricular
BBS	Biospecimen Banking System
b-hCG	beta-human chorionic gonadotropin
BID	twice a day
BMI	body mass index
BP	blood pressure
bpm	beats per minute
BUN	blood urea nitrogen
CFR	Code of Federal Regulations
CI	confidence interval
CIOMS	Council for International Organizations of Medical Sciences
CK	creatine kinase
CKD-EPI	Chronic Kidney Disease-Epidemiology Collaboration
CL/F	apparent clearance of drug from eg, plasma
C last	last observed (quantifiable) plasma concentration
C max	maximum observed plasma concentration
CO 2	carbon dioxide (bicarbonate)
COVID-19	coronavirus disease 2019
CRF	case report form
CRO	contract research organization
CRU	clinical research unit
CSR	Clinical Study Report
CT	clinical trial
CTMS	clinical trial management system
CYP	cytochrome P450

Abbreviation	Term
CYP3A4	cytochrome P450 3A4
CYP3A5	cytochrome P450 3A5
DILI	drug-induced liver injury
DMC	Data Monitoring Committee
EC	ethics committee
ECC	Emergency Contact Card
ECG	electrocardiogram
eCRF	electronic case report form
EDB	exposure during breastfeeding
EDP	exposure during pregnancy
eGFR	estimated glomerular filtration rate
EMA	European Medicines Agency
EU	European Union
EudraCT	European Clinical Trials Database
FDA	Food and Drug Administration
FIH	first-in-human
$f_m$	fraction metabolized
FSH	follicle stimulating hormone
GCP	Good Clinical Practice
GGT	gamma-glutamyl transferase
GLP	Good Laboratory Practice
HBcAb	hepatitis B core antibody
HBsAb	hepatitis B surface antibody
HBsAg	hepatitis B surface antigen
HCoV	human coronavirus
HCoV-229E	human coronavirus 229E
HCoV-HKU1	human coronavirus HKU1
HCoV-NL63	human coronavirus NL63
HCoV-OC43	human coronavirus OC43
HCV	hepatitis C virus
HCVAb	hepatitis C antibody
HIV	human immunodeficiency virus
HR	heart rate
HRT	hormone replacement therapy
IB	Investigator's Brochure
ICD	informed consent document
ICH	International Council for Harmonisation of Technical Requirements for Pharmaceuticals for Human Use
ID	identification
IND	Investigational New Drug
INR	international normalized ratio
IPAL	Investigational Product Accountability Log
IQMP	Independent Qualified Medical Practitioners
IRB	Institutional Review Board
IV	Intravenous(ly)
$k_{el}$	terminal phase rate constant calculated by a linear regression of the log-linear concentration-time curve.

Abbreviation	Term
K i	inhibition constant
LBBB	left bundle branch block
LFT	liver function test
MAD	multiple ascending dose
MCH	mean corpuscular hemoglobin
MCHC	mean corpuscular hemoglobin concentration
MCV	mean corpuscular volume
MERS	Middle East Respiratory Syndrome
msec	millisecond
n	number of participants
N/A	not applicable
NHP	non-human primate
NOAEL	no observed adverse effect level
PCR	polymerase chain reaction
PD	pharmacodynamic(s)
PE	physical examination
pH	potential of hydrogen
PK	pharmacokinetic(s)
PR	pulse rate
PT	prothrombin time
PT-INR	prothrombin time-international normalized ratio
PVC	premature ventricular contraction/complex
q12h	every 12 hours
QT	time from the beginning of the QRS complex to the end of the T wave
QTc	corrected QT interval
QTcF	QTc corrected using Fridericia's formula
qual	qualitative
RBC	red blood cell
R ac	accumulation ratio
R ac,Cmax	accumulation ratio based on C max :
RR	respiratory rate
RT-PCR	reverse-transcriptase polymerase chain reaction
SAD	single ascending dose
SAE	serious adverse event
SAP	Statistical Analysis Plan
SARS-CoV-1	severe acute respiratory syndrome coronavirus 1
SARS-CoV-2	severe acute respiratory syndrome coronavirus 2
SCr	serum creatinine
SoA	schedule of activities
SOP	standard operating procedure
SRSD	single-reference safety document
SUSAR	Suspected Unexpected Serious Adverse Reaction
t ½	terminal elimination half-life
TBili	total bilirubin
TEAE	treatment emergent adverse event
THC	tetrahydrocannabinol
T max	time to reach C max

Abbreviation	Term
TSH	thyroid stimulating hormone
ULN	upper limit of normal
US	United States
USPI	United States Prescribing Information
V z /F	apparent volume of distribution for extravascular dosing
WBC	white blood cell
WHO	World Health Organization
WOCBP	woman/women of childbearing potential

1. VERSION HISTORY

Table 1. Summary of Changes

Version/ Date	Associated Protocol Amendment	Rationale	Specific Changes
1.0 07 Dec 2021	Original 18 Oct 2021	N/A	N/A

2. INTRODUCTION

This is a Phase 1, open-label, single dose, randomized, 2-treatment, 2-sequence, 2-period crossover study to evaluate the effect of a high-fat meal on the relative bioavailability of PF-07321332 boosted with ritonavir following single dose oral administration of PF-07321332 in combination with ritonavir using 150 mg tablet formulation of PF-07321332 in healthy adult participants.

This statistical analysis plan (SAP) provides the detailed methodology for summary and statistical analyses of the data collected in Study C4671019. This document may modify the plans outlined in the protocol; however, any major modifications of the primary endpoint definition or its analysis will also be reflected in a protocol amendment.

2.1. Study Objectives and Endpoints

Objectives	Endpoints
Primary:	Primary:

 To evaluate the effect of a high-fat meal on the exposure of PF-07321332 boosted with ritonavir following a single oral dose of PF-07321332 in combination with ritonavir using 150 mg tablet formulation of PF-07321332. 	
 The ratio of AUC_{last}, AUC_{inf} (if data permit) and C_{max} of PF-07321332.
Secondary:	Secondary:

 To characterize the pharmacokinetic parameters of PF-07321332 boosted with ritonavir following a single oral dose of PF-07321332 in combination with ritonavir. To evaluate the safety and tolerability of PF-07321332/ritonavir in healthy participants. 	
 T_{max}, and $t_{1/2}$, CL/F and V_z/F (if data permit). Assessment of TEAEs, clinical laboratory abnormalities, vital signs, and 12-lead ECGs.

2.2. Study Design

This is a Phase 1, open-label, single dose, randomized, 2-treatment, 2-sequence, 2-period crossover study to evaluate the effect of a high-fat meal on the relative bioavailability of PF-07321332 boosted with ritonavir following single dose oral administration of PF-07321332 in combination with ritonavir using 150 mg tablet formulation of PF-07321332 in healthy adult participants. The study will consist of 2 treatments: a single oral dose of 300 mg PF-07321332 (2 × 150 mg tablets) under fasted conditions and 3 doses of 100 mg ritonavir at -12 hour, 0 hour and 12 hour related to PF 07321332 dosing (Treatment A), and a single oral dose of 300 mg PF 07321332 (2 × 150 mg tablets) under fed conditions and 3 doses of 100 mg ritonavir at -12 hour, 0 hour and 12 hour related to PF-07321332 dosing (Treatment B).

*There will be a total of 2 treatment sequences shown in **Table 2** with the assigned Treatments A or B in each treatment period.*

Table 2. Treatment Sequences

	Period 1	Washout (4 days between PF-07321332 dosing)	Period 2
Sequence 1 (n=6)	Treatment A		Treatment B
Sequence 2 (n=6)	Treatment B		Treatment A

Each enrolled participant will participate in 2 study periods to receive 2 different treatments according to the sequence determined by randomization:

- *Treatment A: Single oral dose of 300 mg PF-07321332 (2 × 150 mg tablets) under fasted conditions and 3 doses of 100 mg ritonavir at -12 hour, 0 hour and 12 hour related to PF-07321332 dosing. (Reference)*
- *Treatment B: Single oral dose of 300 mg PF 07321332 (2 × 150 mg tablets) under fed conditions and 3 doses of 100 mg ritonavir at -12 hour, 0 hour and 12 hour related to PF-07321332 dosing. (Test)*

A total of approximately 12 healthy male and/or female participants will be randomly assigned to investigational product such that approximately 6 participants will be enrolled to each sequence. Participants who withdraw from the study may be replaced at the sponsor's discretion in collaboration with the Investigator.

The total planned duration of participation, from the screening visit to the last Follow-up phone call, is approximately 10 weeks. Participants will be screened within 28 days prior to the first dose of investigational products and if all eligibility criteria are fulfilled, the participants will report to the CRU on Day -1 and will be required to stay in the CRU for 8 days and 7 nights.

3. ENDPOINTS AND BASELINE VARIABLES: DEFINITIONS AND CONVENTIONS

3.1. Primary Endpoint(s)

The primary endpoints are the plasma PK endpoints which are described in Section 3.3.

3.2. Secondary Endpoint(s)

The secondary endpoints related to PK are described in Section 3.3. The secondary endpoints related to safety/tolerability are described in Section 3.5.

3.3. Other Endpoint(s)

Blood samples for PK analysis of PF-07321332 will be collected according to the Schedule of Activities given in the protocol.

Plasma PK parameters of PF-07321332 will be derived (as data permit) from the concentration-time data using standard noncompartmental methods. Actual PK sampling times will be used in the derivation of PK parameters. In the case that actual PK sampling times are not available, nominal PK sampling time will be used in the derivation of PK parameters.

Table 3. Noncompartmental PK Parameters of PF-07321332 to be calculated

Parameter	Analysis Scale	PF-07321332
AUC _{inf} *	ln	A, D
AUC _{last}	ln	A, D
C _{max}	ln	A, D
T _{max}	R	D
t _{1/2} *	R	D
CL/F*	ln	D
V _z /F*	ln	D

*=if data permits.

Abbreviations: A = analyzed using a statistical model; D=displayed with descriptive statistics as outlined in Table 4 in Section 6.1; ln=natural-log transformed; R=raw (untransformed)

T_{last} will also be provided as a support parameter for AUC_{last}. T_{last} values will only be listed and not summarized.

3.4. Baseline Variables

Baseline variables are those collected on Day 1 prior to dosing or before Day 1. Baseline for laboratory data, vital signs and ECG are defined in Sections 3.5.2, 3.5.3 and 3.5.4 respectively.

3.5. Safety Endpoints

3.5.1. Adverse Events

An adverse event is considered a Treatment-Emergent Adverse Event (TEAE) if the event started during the effective duration of treatment. All events that start on or after the first dosing day and time/start time, if collected, but before the end of the study will be flagged as TEAEs. The algorithm will not consider any events that started prior to the first dose date of PF-07321332.

A 3-tier approach for summarizing AEs will not be used due to the low number of participants planned to be recruited.

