## **10.3. Appendix 3: Adverse Events: Definitions and Procedures for Recording, Evaluating, Follow-Up, and Reporting**

### **10.3.1. Definition of AE**

AE Definition

• An AE is any untoward medical occurrence in a patient or clinical study participant, temporally associated with the use of study intervention, whether or not considered related to the study intervention.

• Note: An AE can therefore be any unfavorable and unintended sign (including an abnormal laboratory finding), symptom, or disease (new or exacerbated) temporally associated with the use of study intervention.

Events Meeting the AE Definition

• Any abnormal laboratory test results (hematology, clinical chemistry, or urinalysis) or other safety assessments (eg, ECG, radiological scans, vital sign measurements), including those that worsen from baseline, considered clinically significant in the medical and scientific judgment of the investigator. Any abnormal laboratory test results that meet any of the conditions below must be recorded as an AE:

• Is associated with accompanying symptoms;

• Requires additional diagnostic testing or medical/surgical intervention;

• Leads to a change in study dosing (outside of any protocol-specified dose adjustments) or discontinuation from the study, significant additional concomitant drug treatment, or other therapy.

• Exacerbation of a chronic or intermittent preexisting condition, including either an increase in frequency and/or intensity of the condition.

• New condition detected or diagnosed after study intervention administration, even though it may have been present before the start of the study.

• Signs, symptoms, or the clinical sequelae of a suspected drug-drug interaction.

• Signs, symptoms, or the clinical sequelae of a suspected overdose of either study intervention or a concomitant medication. Overdose per se will not be reported as an AE or SAE unless it is an intentional overdose taken with possible suicidal/self-harming intent. Such overdoses should be reported regardless of sequelae.

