### Events NOT Meeting the AE Definition

- Any clinically significant abnormal laboratory findings or other abnormal safety assessments that are associated with the underlying disease, unless judged by the investigator to be more severe than expected for the participant's condition.
- The disease/disorder being studied or expected progression, signs, or symptoms of the disease/disorder being studied, unless more severe than expected for the participant's condition.
- Medical or surgical procedure (eg, endoscopy, appendectomy): the condition that leads to the procedure is the AE.
- Situations in which an untoward medical occurrence did not occur (social and/or convenience admission to a hospital).
- Anticipated day-to-day fluctuations of preexisting disease(s) or condition(s) present or detected at the start of the study that do not worsen.

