#### **Assessment of Intensity**

The investigator will make an assessment of intensity for each AE and SAE reported during the study and assign it to 1 of the following categories:

- Mild: Asymptomatic or mild symptoms; clinical or diagnostic observations only; intervention not indicated.
- Moderate: Minimal, local or noninvasive intervention indicated; limiting age-appropriate instrumental ADL. Instrumental ADL refers to preparing meals, shopping for groceries or clothes, using the telephone, managing money, etc.
- Severe: Severe or medically significant but not immediately life-threatening; hospitalization or prolongation of hospitalization indicated; disabling, limiting self-care ADL. Self-care ADL refers to bathing, dressing and undressing, feeding self, using the toilet, taking medications, and not bedridden.

An event is defined as “serious” when it meets at least 1 of the predefined outcomes as described in the definition of an SAE, NOT when it is rated as severe.

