#### Follow-Up of AEs and SAEs

- The investigator is obligated to perform or arrange for the conduct of supplemental measurements and/or evaluations, as medically indicated or as requested by the sponsor, to elucidate the nature and/or causality of the AE or SAE as fully as possible. This may include additional laboratory tests or investigations, histopathological examinations, or consultation with other healthcare providers.
- If a participant dies during participation in the study or during a recognized follow-up period, the investigator will provide Pfizer Safety with a copy of any postmortem findings, including histopathology.
- New or updated information will be recorded in the originally submitted documents.
- The investigator will submit any updated SAE data to the sponsor within 24 hours of receipt of the information.

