5.2. General Methods

Unless otherwise stated, all summaries and plots will be presented by treatment.

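### The TEAE rule in SAP 3.5.1 tests only when an event started, so an AE on record before dosing that worsens afterwards is left out unless it is re-entered as a new event

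*SAP*

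**What the plan says.** SAP 3.5.1 sets the rule in three sentences, and all three turn on the start of the event. The general statement is "An adverse event is considered a Treatment-Emergent Adverse Event (TEAE) if the event started during the effective duration of treatment". The events to be flagged are then described as "All events that start on or after the first dosing day and time/start time, if collected, but before the end of the study". The third sentence is an exclusion: "The algorithm will not consider any events that started prior to the first dose date of PF-07321332". Severity, frequency and seriousness play no part.

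The protocol collects AEs from an earlier point. Section 8.3.1 opens active collection at informed consent, and the Schedule of Activities shows AE monitoring from the screening visit, which may fall up to 28 days before dosing.

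Section 10.3.1 (Appendix 3) lists among the events that meet the AE definition: "Exacerbation of a chronic or intermittent preexisting condition, including either an increase in frequency and/or intensity of the condition". The companion list of events that do not qualify removes only "Anticipated day-to-day fluctuations of preexisting disease(s) or condition(s) present or detected at the start of the study that do not worsen".

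Section 10.3.3 asks the investigator for an "assessment of intensity for each AE and SAE reported during the study and assign it to 1 of the following categories". Its follow-up text adds: "New or updated information will be recorded in the originally submitted documents".

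TEAEs are part of a named secondary endpoint (protocol section 3, SAP 2.1). SAP 5.2 states: "Unless otherwise stated, all summaries and plots will be presented by treatment". SAP 6.6.1, on adverse events, names the analysis set and nothing more.

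**The concern.** Worsening after a dose is one of the things a tolerability summary is meant to show. The protocol regards an increase in intensity as reportable, but the SAP gives it no role in deciding what is treatment-emergent. If a participant has a mild headache on record before dosing and it becomes severe afterwards in the same record, the stated algorithm does not consider it.

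The SAP treats its other safety data differently. For laboratory tests, vital signs and ECG (SAP 3.5.2 to 3.5.4) it defines a pre-dose baseline and judges later values against it. AEs have no counterpart.

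The AE sections also do not defer to the sponsor's reporting standards, as the laboratory, disposition and demographic sections do. SAP 5.3 invokes sponsor rules for safety data only for imputation. The gap is therefore not closed elsewhere in the SAP.

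**Working it through.** The plan gives no figure to reproduce: there is no stated AE rate, and no hypothesis test is planned (SAP 5.1). The check is to run the rule over the ways in which an event can meet the first PF-07321332 dose.

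1. **Event starts after the dose.** It is flagged.
2. **Condition present before consent, worsens after the dose, entered as an AE with a post-dose start.** Appendix 3 allows this entry, and the start falls inside the window. It is flagged.
3. **AE starts between consent and the first dose date, worsens after the dose, and a new entry is opened for the rise.** The new entry has a post-dose start. It is flagged.
4. **Same event as in 3, but the rise is kept in the existing entry.** The start date remains before dosing. The flagging sentence does not reach it and the exclusion sentence removes it. It is not flagged.

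Case 4 is the gap. Whether an event falls into case 3 or case 4 depends on how the site enters a rise in intensity, and neither document states a rule for that.

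**Direction.** Over the four cases the rule either flags a post-dose worsening or drops it. It never adds an event that a worsening condition would leave out. The error is therefore zero or negative in the TEAE count.

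**Size per participant.**
- Inputs: approximately 12 participants (protocol 9.5), each receiving both treatments (protocol 4.1), so about 12 per treatment.
- Formula: change in incidence = 1 / participants per treatment.
- Result: 1/12 = 0.083, or 8.3 percentage points.

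This is the most that one participant can move a treatment's incidence. If that participant already has another TEAE under the same treatment, only the event count changes.

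**Frequency.** It cannot be derived from the documents. An affected event must start after consent, still be present at dosing, worsen afterwards, and not be re-entered.

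**Dose that opens the window.** Ritonavir is first given on the evening of Day -1, before the first PF-07321332 dose. Moving the cut-off to that dose would leave case 4 in place for events that started earlier still.

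**The case against.** The strongest reply is that Appendix 3 already provides the route. An exacerbation is an AE in its own right, only fluctuations without worsening are excluded, and an exacerbation entered with a post-dose start is flagged under SAP 3.5.1 as written. The intensity and follow-up text in section 10.3.3 does not lay down one record per event: it says nothing on start dates or on splitting an entry when the grade rises. Protocol 10.1.6 leaves CRF instructions to a separate completion document, which may already require a new entry. Participants are healthy, safety is descriptive, every AE from consent is recorded on the CRF, and an event that becomes serious during active collection is reported whether or not it is a TEAE.

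Much of this stands. A reader might infer that worsening of an existing event is never counted. The documents do not support that, because of cases 2 and 3 above. Nor is it exact to say that only the onset date matters, since the start time is used if collected.

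Two things survive. First, the Appendix 3 entry speaks of long-standing or recurring conditions and does not plainly cover an acute AE first recorded between consent and dosing. That is the likelier case here, because exclusion criterion 2 removes clinically significant disease. Second, an endpoint definition should not depend on an entry convention that the SAP does not state.

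A reader might also infer that an event which starts in Period 1 and worsens in Period 2 is counted under the wrong treatment. The documents do not show this. SAP 5.2 says only that summaries are by treatment, SAP 4 that participants are analysed by what they actually received, and SAP 6.6.1 names only the analysis set. No text assigns an AE to a period by its start or by anything else. What can be said is that the attribution rule is missing.

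Finally, multiplying the screening window by the sample size (28 days x 12 = 336 participant-days) gives an upper bound on collection time before dosing. It does not measure how often the problem would arise.

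**Conclusion.** The point holds in a limited form. SAP 3.5.1 defines TEAEs solely by event start and excludes events that began before the first PF-07321332 dose date, with no condition for worsening. An AE on record before dosing that worsens afterwards, and is not re-entered as a new event, is left out of a secondary endpoint, and the error can only lower the count.

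The conclusion assumes that at least some rises in intensity stay in the original entry; the documents neither require nor prevent this. The number of such events is unknown and probably small. One affected participant is worth up to 8.3 percentage points of a treatment's incidence, on about 12 participants per treatment. The primary pharmacokinetic analysis is not touched.

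The absence of a rule for assigning AEs to a crossover period is a secondary clarification. It is not evidence that events will be misattributed.

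**What to change.** In SAP 3.5.1, add that an event which began before first dosing and increases in severity or becomes serious after it is also flagged as a TEAE. Qualify the exclusion sentence so that it does not override this.

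Have sites record the rise as a new AE entry with its own start date and time, so that the condition can be programmed. If the CRF completion guidance already requires this, a reference to it in the SAP is enough.

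When the rule for assigning AEs to a period and treatment is written, state that a worsening recorded in Period 2 is assigned to the Period 2 treatment.

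The cost is a few sentences in the SAP, one programming condition and at most one instruction to sites. The downside is a few extra AE records and slightly higher event counts, because an event that worsens can give two entries. The design and the primary analysis do not change.
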